4.7.2.3 Summary of excess Hb response from baseline to week 6 and beyond

The analysis population for efficacy will be MITT and PP population. The following summary will be provided:

- A summary of subject with three excess Hb criteria: Hb>13 g/dL, Hb>12 g/dL to 13 g/dL and >1 g/dL increment in a 2-week period will be provided by treatment group on 2-week basis starting from baseline to week 18. In addition, the period starting from baseline to week 16, primary efficacy period (baseline to week 6) and dose adjustment and maintenance period (week 7 to week 16) will also be presented within three excess HB criteria.

4.7.3 Secondary Efficacy Variables

The analysis population for efficacy will be MITT and PP population.

Change from baseline visit to Week 6 in HB (g/dL).

The following summaries will be provided:

- A summary of actual value of Hb by treatment group at baseline and week 6. A summary of the change (absolute and percent) from baseline in Hb by treatment group at week 6. 1st and 3rd quartiles (Q1, Q3) as well as the mean, SD, median, minimum, maximum and number of observations will be shown. P values for overall comparison and treated groups vs. placebo on change from baseline will also be presented.
- The effect of treatment in terms of the change from pre-treatment to Week 6 in Hb will be analyzed using a one-way analysis of covariance (ANCOVA). The statistical model will assess the main effect of treatment, adjusted for Baseline. Least-squares (LS) means for each treatment and their 95% confidence intervals (CIs) will be

presented. Three post-hoc pairwise comparison, i.e., Placebo vs 150 mg, placebo vs 300 mg, and placebo vs 600 mg, will be done. Unadjusted one-way analysis of variance (ANOVA) will be performed for sensitivity.

- The simple linear regression between the change from Baseline to Week 6 in Hb and dose will be calculated. The regression coefficients and their standard errors, p-values of test of regression parameters and their 95% CIs will be presented. The test of slope parameter will be used to evaluate dose response relationship.
- A waterfall plot for absolute Hb change from baseline for each treatment group at week 6.
- A summary of the number and percentage of subjects who achieved a ≥ 1 g/dL increase in Hb from baseline average will be provided by treatment group.

Time to reach target Hb level

Time to reach target Hb level of 10.0-12.0 g/dL from baseline is defined for subjects with Hb <10.0 g/dL at the baseline visit as following:

First post-treatment assessment date with value of Hb ≥ 10.0 and ≤ 12.0 g/dL – the baseline visit date +1. If target Hb level is not achieved, last Hb assessment date will be used as censored date.

A summary of time to reach target Hb level will be provided for subjects with Hb <10.0 g/dL at the baseline visit by treatment group.

A by-subject listing will be provided.

Hb within target Range

A summary of the number and percentage of subjects within target Hb 10-12 g/dL at the end of the dose adjustment and maintenance period (Week 16) will be provided by treatment group.

The number and percentage of subjects above / within / below target range who are maintained within the target range at their previous visit after Week 6 will be provided by treatment group.

The effect of treatment in terms of the proportion of subjects within target Hb level at Week 6 will be analyzed using Fisher's exact test. Three post-hoc pairwise comparison, i.e., placebo vs 150 mg, placebo vs 300 mg, and placebo vs 600 mg, will be done.

A by-subject listing will be provided.

Increase in Hb from pre-treatment average

A summary of the cumulative number and percentage of subjects who achieved a ≥ 1 g/dL increase in Hb from pre-treatment average will be provided by treatment group. In addition, the cumulative proportion of subjects within target range will be displayed graphically from baseline visit to follow up visit by treatment group.

The effect of treatment in terms of the proportion of subjects who achieved a ≥ 1 g/dL increase in Hb from pre-treatment average will be analyzed using Fisher's exact test. Three post-hoc pairwise comparison, i.e., Placebo vs 150 mg, placebo vs 300 mg, and placebo vs 600 mg, will be done.

Hematocrit, RBC count, and reticulocyte count (CBC)

Hematocrit, RBC count, and reticulocyte count (both absolute and percent) will be analyzed as secondary efficacy variables.

The following summaries will be provided:

- A summary of hematocrit, RBC count, and reticulocyte count (both absolute and percent) by treatment group and time point. 1st and 3rd quartiles (Q1, Q3) as well as the mean, SD, median, minimum, maximum and number of observations will be presented.
- A summary of the change (absolute and percent) from baseline in hematocrit, RBC count, and reticulocyte count (both absolute and percent) by treatment group and time point.
- Box plots of absolute changes from baseline in hematocrit, RBC count, and reticulocyte count for each treatment group at each post-treatment time point.

The effect of treatment in terms of the change from baseline to Week 6 in hematocrit and RBC count and reticulocyte count (both absolute and percent) will be analyzed using ANCOVA. The statistical model will assess the main effect of treatment, adjusted for baseline measurement. LS-means for each treatment and their 95% CIs will be presented. Three post-hoc pairwise comparison, i.e., Placebo vs 150 mg, placebo vs 300 mg, and placebo vs 600 mg, will be done. Unadjusted ANOVA will be performed for sensitivity.

A by-subject listing of hematocrit, RBC count, and reticulocyte count (both absolute and percent) will be provided by treatment group.

Iron indices and hepcidin

Iron indices (i.e., iron, TIBC, TSAT, and ferritin) and hepcidin will be analyzed as secondary efficacy variables.

The following summaries will be provided:

- A summary of iron indices and hepcidin by treatment group and time point
- A summary of the change (absolute and percent) from baseline in iron indices and hepcidin by treatment group and time point
- Box plots of absolute changes from baseline in iron indices and hepcidin for each treatment group at each post-treatment time point

A by-subject listing of iron indices and hepcidin will be provided by treatment group.

Rescue therapy & ESA administration

Initiation of rescue therapy will be analyzed.

The following Rescue therapy summaries will be provided:

- A summary of the number and percentage of subjects requiring rescue with RBC transfusion from baseline to the end of the primary efficacy period (Week 6) and the end of the dose adjustment and maintenance period (Week 16)
- A summary of the number and percentage of subjects requiring rescue with ESAs from baseline to the end of the primary efficacy period (Week 6) and the end of the dose adjustment and maintenance period (Week 16) An ESA rescue is defined to fulfill the following 4 criteria simultaneously:
 1. ESA administration, and
 2. ESA administered because the subject experienced a clinically significant worsening of their anemia or symptoms of anemia, and
 3. ESA administered because the subject's Hb level is <9.0 g/dL, and
 4. Subjects' reason for early study withdrawal is because of "Worsening of anemia requiring ESA rescue or blood transfusion".

The following ESA administration summaries will be provided:

- A summary of the number and percentage of subjects requiring administration with ESAs from baseline to the end of the primary efficacy period (Week 6) and the end of the dose adjustment and maintenance period (Week 16)

The effect of treatment in terms of the proportion of subjects requiring RBC transfusion / ESAs administration will be analyzed using Fisher's exact test. Three post-hoc pairwise comparison, i.e., Placebo vs 150 mg, placebo vs 300 mg, and placebo vs 600 mg, will be done.

By-subject listings of rescue therapies and ESA administration will be provided by treatment group.

Average Daily Dose

A summary of Average Daily Dose by treatment group and visit will be presented with 1st and 3rd quartiles (Q1, Q3) as well as the mean, SD, median, minimum, maximum and number of observations.

Dose adjustment

A overview summary of the number of dose adjustments from baseline to the end of the dose adjustment and maintenance period (Week 16) will be provided.

A summary of the number of dose adjustments by visit from baseline to the end of the dose adjustment and maintenance period (Week 16) will be provided.

A by-subject listing of dose adjustment with HB change will be provided by treatment group. The three flags of HB change will be presented as follows:

- HB >13 g/dL at any time of study
- HB >12 g/dL to 13 g/dL at dose adjustment and maintenance period only
- HB increase >1 g/dL over 2 weeks at any time of study.

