## 11.2 Primary Efficacy Analysis and Sample Size Determination

An analysis of covariance (ANCOVA) model will be used to compare change from pre-treatment in Hb between the three vadadustat dosing groups and the placebo group. The model will include treatment assignment (3 dosed groups and one placebo group) and pre-treatment Hb value as a covariate. A step-down procedure will be used to control the overall type I error rate for the multiple comparisons. Testing of the highest dose compared with placebo will be conducted first. If and only if this comparison is significant, then testing will proceed to comparison of the next lower dose and placebo, and so on. Thus, no multiplicity adjustment will be needed for this analysis.

The sample size and power calculations are based on results from Study AKB-6548-CI-0005 that was conducted in the United States and evaluated vadadustat in patients with anemia secondary to non-dialysis-dependent CKD. It is reasonable to extrapolate these data to the current study based on the following findings:

- PK parameters of vadadustat are similar between CKD patients who are receiving hemodialysis (Study AKB-6548-CI-0009) and CKD patients who are not receiving dialysis (Study AKB-6548-CI-0003)
- Hemodialysis procedure has no significant impact on the PK of vadadustat (Study AKB-6548-CI-0009)
- The dose range of 150-600 mg of vadadustat to be used in the current study has been shown to be generally well-tolerated, and efficacious in raising and/or maintaining Hb at the desired target level in CKD patients who were either on hemodialysis (Study AKB-6548-CI-0011) or CKD patients who were not on dialysis (Studies AKB-6548-CI-0005 and AKB-6548-CI-0007)

The target enrollment will be approximately 48 subjects for the study with 12 subjects enrolled in each of the 4 treatment groups.

The study is powered based on a comparison of the highest dose vadadustat group (600 mg daily) and the placebo group.

Based on the results from Study AKB-6548-CI-0005 that was conducted in the United States and evaluated vadadustat in patients with anemia secondary to NDD-CKD, it is assumed that the expected mean Hb changes from pre-treatment to Week 6 will be approximately 0 mg/dL for the placebo group and 1.35 g/dL for the highest dose vadadustat group (600 mg daily).

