Based on the results from Study AKB-6548-CI-0011 that was conducted in the United States and evaluated vadadustat in patients with anemia secondary to DD-CKD, it is assumed that the common Hb standard deviation will be 0.9 g/dL across treatment groups. In addition, a dropout rate of 10% is assumed. With these assumptions, the study with n=12 subjects per group will have >85% power to detect the difference between treatment group and control group, at 2-sided alpha of 0.05.

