2 STUDY OBJECTIVES

2.1 Primary Objective and Endpoint

The primary objective of this study is to assess the dose-response relationship between oral vadadustat once daily dosing for 6 weeks and the change in Hb in Japanese subjects with anemia secondary to DD-CKD; this is to define the starting dose for use in Phase 3 clinical studies in Japan.

The primary endpoint that will be used to assess this objective is the mean change in Hb levels from pre-treatment to the end of the primary efficacy period (Week 6). Pre-treatment Hb is defined as the average of 3 Hb values obtained prior to treatment based on 2 qualifying screening Hb values and the Hb value at the baseline visit (Day 1).

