4.7 Efficacy Evaluation

4.7.1 Analysis and Data Conventions

This study is designed to test for dose-response relationship. An analysis of covariance (ANCOVA) model will be used to compare absolute change from pre-treatment in Hb between the 3 vadadustat dosing groups and the placebo group. The model will include treatment assignment (3 dosed groups and one placebo group) and pre-treatment Hb value as a covariate. A step-down procedure will be used to control the overall type I error rate for the multiple comparisons. Testing of the highest dose compared with placebo will be conducted first. If and only if this comparison is significant, then testing will proceed to comparison of the next lower dose and placebo, and so on. Therefore, no multiplicity adjustment will be needed for this analysis.

A linear regression dose-response modeling will be performed as a secondary analysis.

$$Y = \beta_0 + \beta_{dose}X$$

where Y is change in Hb and X is vadadustat dose. β_x s are parameters of the model. β_0 is intercept and β_{dose} is slope, respectively.

The null hypothesis for the dose response will be that the regression coefficient of slope parameter is zero. The alternative hypothesis will be that the regression coefficient is not zero. Symbolically, this is expressed as follows:

$$\begin{aligned} H_0: \beta_{dose} &= 0 \\ H_1: \beta_{dose} &\neq 0 \end{aligned}$$

This hypothesis will be tested using a 0.05 two-sided significance level.

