4.10 Determination of Sample Size

The target enrollment will be approximately 48 subjects for the study with around 12 subjects enrolled in each of the 4 treatment groups.

The study is powered based on a comparison of the highest dose vadadustat group (600 mg daily) and the placebo group. Based on the results from Study AKB-6548-CI-0005 that was conducted in the United States and evaluated vadadustat in patients with anemia secondary to DD-CKD, it is assumed that the expected mean Hb changes from baseline to Week 6 will be approximately 0 mg/dL for the placebo group and 1.35 g/dL for the highest dose vadadustat group (600 mg daily), with a common standard deviation of 0.68 g/dL across treatment groups. With these assumptions, the study with n=12 subjects per group will have >95% power to detect the difference between treatment group and control group, at 2-sided alpha of 0.05.

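### The ≥1 g/dL Hb-responder proportion is tested without using dose order and without a stated time point; a Week 6 exact trend test, added alongside the planned Fisher tests, would be a cheap supportive gain

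*SAP*

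**What the plan says.** The SAP describes the aim plainly. Section 2.1: "The primary objective of this study is to assess the dose-response relationship between oral vadadustat once daily dosing for 6 weeks". Section 4.7.1: "This study is designed to test for dose-response relationship". For continuous Hb change it plans a step-down ANCOVA and a linear regression on dose (4.7.1, 4.7.2.1).

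For the responder proportion (a rise of at least 1 g/dL from the pre-treatment average), SAP 4.7.3 first specifies Fisher's exact test for the effect of treatment. It then adds the SAP's standard follow-up sentence: "Three post-hoc pairwise comparison, i.e., placebo vs 150 mg, placebo vs 300 mg, and placebo vs 600 mg, will be done". The plain reading is an overall four-group test plus three pairwise tests. No trend test for a proportion appears anywhere in the SAP.

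The responder summary is described as cumulative, and no visit is named for the Fisher test. By contrast, the target-range paragraph in the same section does name Week 6 for its Fisher test.

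The responder proportion is not in the endpoint lists of Protocol 5.2 or SAP 2.2. SAP 4.7.1.4 treats secondary variables as supportive of the primary objective, and no power is claimed for this one.

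**The concern.** A supportive analysis for a dose-response objective should be able to use the dose ordering. The overall Fisher test treats the four arms as unordered labels. Each pairwise test uses half the subjects, and Fisher's test is conservative at this size: 1/11 on placebo against 6/11 on 600 mg gives a two-sided p of 0.063. A responder pattern that rises steadily with dose could therefore be reported as three non-significant comparisons.

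The missing time point matters separately. Under Protocol 8.2.5 placebo subjects move to vadadustat at the Week 6 visit and doses are then titrated. A placebo comparison of responders counted after Week 6 would no longer compare the randomised doses with placebo. Fixing the visit is needed whichever test is used.

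**Working it through.** **Inputs from the documents**
- 12 per arm (Protocol 11.2). "In addition, a dropout rate of 10% is assumed". So 12 × 0.9 = 10.8, about 11. Secondary endpoints are analysed as observed (SAP 4.7.1.3).
- Mean change 0 on placebo and 1.35 g/dL on 600 mg (Protocol 11.2; the placebo unit is corrected to g/dL in the note to file of February 2017).
- SD, protocol: "it is assumed that the common Hb standard deviation will be 0.9 g/dL across treatment groups". SD, SAP 4.10: "with a common standard deviation of 0.68 g/dL across treatment groups". The two conflict, so both are run.
- Two-sided alpha 0.05.

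**Assumptions**
- Middle-dose means, which the current plan does not give. Either linear in dose (1.35 × 150/600 = 0.3375 and 1.35 × 300/600 = 0.675), or 0.5 and 0.7, borrowed from the superseded Version 1 assumptions.
- Normal changes, and response defined at the Week 6 visit.
- Dose reductions before Week 6 are not modelled.

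**Step 1: the plan's own figure (mean change, 600 mg versus placebo).** The protocol says the study "will have >85% power to detect the difference between treatment group and control group, at 2-sided alpha of 0.05". The noncentrality is 1.35 / (SD × √(2/n)).
- SD 0.9, n = 11: 1.35 / 0.384 = 3.52 on 20 df, power 91.7%.
- SD 0.9, n = 12: power 93.9%.
- SAP variant, SD 0.68, n = 12: 1.35 / 0.278 = 4.86 on 22 df, power 99.6%.

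The stated lower bounds (above 85% and above 95%) both hold.

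**Step 2: response rates.** P(response) = Φ((mean − 1)/SD). With SD 0.9 and linear means:
- placebo Φ(−1.11) = 13.3%
- 150 mg Φ(−0.74) = 23.1%
- 300 mg Φ(−0.36) = 35.9%
- 600 mg Φ(0.39) = 65.1%

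**Step 3: power by full enumeration.** Fisher power is the summed binomial probability of all 2×2 tables with two-sided p ≤ 0.05. The trend statistic is T = Σ dose × responders, referred to its exact distribution given the total number of responders. Two-sided p counts tables at least as far from the conditional mean.

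| Scenario | Fisher, 600 mg vs placebo | Exact trend, four arms |
|---|---|---|
| n = 11, SD 0.9, linear | 57.6% | 77.9% |
| n = 11, SD 0.9, middle means 0.5/0.7 | 57.6% | 73.7% |
| n = 11, SD 0.9, means 0/0.2/0.5/1.0 | 28% | 52% |
| n = 10, SD 0.9, linear | 48.4% | 75% |
| n = 12, SD 0.9, linear | 66.0% | 81.7% |
| n = 11, SD 0.68, linear | 81.8% | 94.3% |
| n = 11, SD 0.9, plateau (all doses 1.35) | 57.6% | 51% |

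Other results at n = 11, SD 0.9:
- Fisher at 300 mg has about 10–11% power and at 150 mg about 2–5%, over the linear and 0.5/0.7 means.
- The overall four-group Fisher test has 54.9% (0.5/0.7) to 58.8% (linear).
- Doubling the smaller tail instead lowers the trend figures by 2 to 3 points.
- The trend test's type I error is 3.6% when all arms have the placebo rate.

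**Step 4: the planned slope test on continuous Hb change.** By simulation with n = 11 and SD 0.9, power is about 93% (0.5/0.7) to 95% (linear).

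**The case against.** The strongest reply is that the ordered question is already answered, and better, elsewhere. The slope on continuous Hb change has more power than the trend test on a dichotomised version of the same measurement. That stands. It limits this point to a minor supportive improvement.

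A pairwise contrast and a trend also answer different questions. A significant trend does not say which dose works, and the stated purpose is to define a Phase 3 starting dose. That stands too: the trend test does not repair the weak comparisons at 150 and 300 mg, and it cannot replace them. In the plateau case it is the weaker test (51% against 58%).

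The figures depend on the SD. With the SAP's 0.68, Fisher's test at 600 mg has 82% power, so describing it as close to a coin toss would be wrong under the SAP's own input. The trend test remains ahead in the graded scenarios.

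Three stronger readings might tempt a reader, and none is supported:
- That the trial has only about 58% power for dose-response. That figure belongs to one contrast on one supportive binary variable.
- That only pairwise tests are planned. SAP 4.7.3 specifies an overall Fisher test first, although it too ignores dose order.
- That the lower doses will be non-significant whatever the truth. Their low power follows from the assumed modest effects; a 300 mg effect of 1.35 g/dL would have the same 58% as 600 mg.

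**Conclusion.** The concern holds as a low-cost improvement, not as a flaw in the trial's dose-response test. The planned responder tests ignore dose order and have no time point. Under graded monotone responses with 600 mg at 1.35 g/dL, about 11 evaluable per arm and SD 0.9, the exact trend test has roughly 16 to 20 points more power than Fisher's test of 600 mg against placebo (73.7 − 57.6 and 77.9 − 57.6). With SD 0.68 and linear means the gap is about 12 points (94.3 − 81.8).

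These figures rest on assumed middle-dose means, normality, no modelling of dose reductions, and response at the Week 6 visit. They do not apply to a count accumulated over visits, which would raise the rates in every arm, including placebo. The mismatch in SD and stated power between Protocol 11.2 and SAP 4.10 should be reconciled separately.

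**What to change.** In SAP 4.7.3, under the increase in Hb from pre-treatment average:
- Define response for testing as a rise of at least 1 g/dL at the Week 6 visit, by randomised group. Apply this time point to the planned overall and pairwise Fisher tests, which stay.
- Add an exact two-sided Cochran-Armitage trend test (scores 0, 150, 300, 600) on the same response, labelled as a supportive dose-response analysis. State which two-sided definition is used.
- Do not extend the trend test to the proportion within 10–12 g/dL, where overshoot at the top dose can break monotonicity.

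This should be in place before unblinding for the preliminary Week 6 analysis. The cost is a short SAP addition and a standard software option. The downside is one more supportive p-value, and a loss of power if response plateaus from the lowest dose or falls at the top dose. The retained Fisher tests and the response rates by arm would show such a pattern.

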4.7.4 Exploratory Efficacy Variable

Time in Therapeutic Range (TTR) for Hb from week 6 to week 20

The half-time interpolation method will be used to calculate TTR for Hb. The total time of follow-up with Hb in target range of 10.0 to 12.0 g/dL is divided by the total time. Half the time between two tests is allocated to the first Hb value, and half to the second Hb value.

A summary of TTR for Hb will be provided by treatment group.

A by-subject listing of TTR for Hb will be provided by treatment group

